A chest xray will be obtained as clinically indicated following the procedure if there is concern for the development of pneumothorax.

Self-reported pain will be measured using the verbal NRS, a 0-10 ordinal scale (e.g., 0 = "no pain"; 10 = "worst pain imaginable").²⁷ Breakthrough opioid dosing

will be guided by a formal inpatient analgesia protocol. Pain assessments will occur every 6 hours or per standard of care for the appropriate setting (e.g., intensive care unit, trauma ward) for the first 96 hours. All opioid dosing will be converted to oral morphine equivalents for comparison purposes. Time to first breakthrough opioid dose will be recorded. Incentive spirometry will be used and assessed and recorded by respiratory therapist, with adjunct inspiratory assistance (e.g., EzPAP) applied per our institutional volume expansion protocol.

Follow-up will occur daily by study coordinators and trauma service physicians for the first 96 hours after block procedure, then daily by the trauma service physicians for 14 days or until discharge from the hospital if it occurs earlier.

Standard of care analgesia regimen on the trauma service will be provided to all patients enrolled in the study, regardless of liposomal bupivacaine or placebo injection. This regimen will be per the Trauma acute multimodality pain management protocol (Appendix).

Typical escalation of analgesics provided for these patients, as deemed medically appropriate based on age and comorbid medical conditions, includes (in order of addition to regimen):

- Acetaminophen, oral or enteral
- NSAIDs, ibuprofen or ketorolac
- Lidocaine 5% transdermal patch
- Oral or enteral tramadol
- Oral or enteral hydrocodone or oxycodone
- IV morphine or hydromorphone, intermittent dosing
- Patient controlled analgesia morphine or hydromorphone
- Long-acting narcotics, including methadone, oxycodone ER, or morphine ER
- Neuromodulating adjuncts, including gabapentin or pregabalin
- Epidural analgesia catheter placement

During this time all adverse events will be recorded. Subjects who experience serious adverse events will be followed until the event resolves. If necessary these patients will be followed up by weekly phone calls as well as at the standard of care clinic visit two weeks post-discharge.

Randomization

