There may be temporary pain or local discomfort associated with repeated intercostal injections. Additionally, there will be a small risk of a pneumothorax if the intercostal injection needle violates the parietal pleura.

Additionally, the trauma team will have discretion to hold or stop enoxaparin doses if patient is deemed to have bleeding. Patients may also have doses held due to perioperative plans. This will also allow for appropriate, safe patient care.

If a patient enrolled in the study should have an adverse event during the course of the intercostal rib block administration and the reaction is severe or life threatening, then the patient will be withdrawn from the study and no further injections will be administered, regardless of how many injections were originally planned. In addition, an adverse event based on physiologic response will include a sustained (greater than five minute) change in heart rate by > 40% from baseline or absolute heart rate greater than 160 or less than 50, change in systolic blood pressure by 40% or absolute systolic blood pressure less than 80 mmHg or greater than 180 mmHg, change in respiratory rate by 50% or absolute respiratory rate greater than 30 or less than 6, or decreasing oxygen saturation

by 10% SpO₂ or less than absolute SpO₂ < 85%. Any non-sinus rhythm or ST segment changes seen on the EKG monitoring strip will lead to immediate subject discontinuation.

Safety Assessments

Every adverse event, whether or not thought to be related to study drug, will be recorded and entered into the RAVE Case Report Form database.

Any medical condition present prior to study enrollment should not be reported as an adverse event, unless the medical condition worsens in severity or seriousness during the study. In this case it may be reported as an adverse event at the discretion of the Investigator.

The Investigator will review each event and assess its severity and relationship to the study treatment.

Adverse event Definitions:

Adverse Event

Adverse event means any untoward medical occurrence associated with the use of a drug in humans, whether or not considered drug related.

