Myalgia	No interference with activity	Some interference with activity	Significant; prevents daily activity	ER visit or hospitalization

Table 9.4 extracted from: Guidance for Industry, Toxicity Grading Scale for Healthy Adult and Adolescent Volunteers Enrolled in Preventive Vaccine Trials, U.S. Department of Health and Human Services, Food and Drug Administration, Center for Biologics Evaluation and Research, August 2016

Treatment of cardiovascular and neurologic adverse events

- Local anesthetic systemic toxicity
 - Treatment will be initiated as recommended as the American Society of Regional Anesthesia and Pain Medicine, according to the society's checklist (Appendix)
- Treatment will include: transfer to intensive care unit setting if not already in intensive care unit, continuous hemodynamic monitoring for at least 24 hours, appropriate airway management with assistance from respiratory therapy and a critical care consultant as needed, cardiovascular stabilization and assistance from a critical care consultant as needed, administration of Lipid Emulsion therapy, as per ASRA checklist in Appendix, Neurology consult for any observed systemic neurologic toxicity (including change in vision, mental status change, persistent headache, seizure), Cardiology consult for any arrhythmias that persist greater than 30 minutes, beyond initial appropriate medical treatment, or result in hypotension with systolic blood pressure < 80mmHg.

10. Data Safety monitoring plan and/or DSMB:

Patients will be screened for the adverse events described above.

Adverse events will be continuously assessed on an ongoing basis by [name], medical monitor. Study will be stopped if:

- **Adverse events probably/likely or certainly related to study drug, regardless of severity, occur in > 10% of enrolled patients, or**
- **Serious/life-threatening adverse events, regardless of causality, occur in > 2% of enrolled patients.**

11. Data Analysis:

Primary Endpoint

- 1) Compare opioid requirements (in morphine equivalents) between trauma patients with rib and/or sternal fractures receiving liposomal bupivacaine versus standard of care.

Secondary Endpoints

- 1) Compare clinical outcomes and treatment failures including:
 - a. Development of pneumonia, defined as >100,000 cfu/mL bacteria on bronchoalvelolar lavage, or clinically with leukocytosis, pulmonary infiltrate and fever
 - b. Median patient analgesic score by verbal NRS

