This project will use Medidata Rave® as its Electronic Data Capture (EDC) software, which is a robust EDC platform for capturing, managing and reporting clinical research data. This system includes a robust query management system based on the Data Quality Plan, which will identify data quality checks to be programmed into the database design. Frequent monitoring of the database throughout the study will allow for corrective action to be taken quickly if problems are identified with the data collection process. The database will be password protected and appropriately secured such that only authorized study personnel will have access to the data. Data will be maintained in a confidential manner with regular reminders of the need for confidentiality provided from the senior investigator. A single subject log will be kept by the principal investigators for matching patient study number, initials, medical record number, and admission date (attached). Once assigned to the log, patients will only be evaluated using their de-identified, study number. Data entered into the electronic database will be de-identified.

Once the study has been completed, the subject log will be destroyed and only the de-identified electronic database will be kept. Only study personnel will have access to the data.

13. Study Population

UCMC is an urban, academic American College of Surgeons-verified Level 1 trauma center that treats over 3500 trauma patients each year. Patients admitted to the UCMC trauma service are eligible for enrollment. Patients will be screened on admission or identified per the daily trauma census. Trauma team

physicians may also contact study personnel daily once a patient is identified as a potential candidate. Study personnel will screen subjects for inclusion and exclusion. If patient meets inclusion criteria, then consent will be administered by study personnel (see section 14).

Inclusion Criteria

- a. Patients with an anticipated length of stay of at least 72 hours
- b. Trauma patients with two or more rib or sternal fractures
- c. Patients demonstrating the inability to achieve greater than 50% predicted inspiratory capacity based on ideal body weight using IS within the first 24 hours of admission (Appendix)
- d. Adults age 18 and older

Exclusion Criteria

- a. Patients with a known allergy to bupivacaine
- b. Respiratory failure requiring intubation within 24 hours prior to enrollment

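### Worsening of a condition present at enrolment is reportable only at the investigator's discretion, which conflicts with the rule that every adverse event is recorded and can keep serious worsening out of the stopping-rule counts

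*Combined protocol and SAP*

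**What the plan says.** Section 9, Safety Assessments, opens with a rule that has no exceptions: "Every adverse event, whether or not thought to be related to study drug, will be recorded and entered into the RAVE Case Report Form database". Section 6 says the same of the follow-up period: "During this time all adverse events will be recorded". The definition in Section 9 is equally broad: "Adverse event means any untoward medical occurrence associated with the use of a drug in humans, whether or not considered drug related".

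Between the recording rule and the definition stands a paragraph on pre-existing conditions. A condition present before enrolment is not to be reported "unless the medical condition worsens in severity or seriousness during the study". The next sentence governs what happens when it does worsen: "In this case it may be reported as an adverse event at the discretion of the Investigator".

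Section 10 has two stopping rules. One counts events judged probably or certainly related to study drug (more than 10% of enrolled patients). The other reads: "Serious/life-threatening adverse events, regardless of causality, occur in > 2% of enrolled patients".

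**The concern.** The discretion applies to whether a worsened condition becomes an adverse event at all. It is not about grading, because Section 9 separately asks the investigator to assess the severity and relationship of each event. The clause also expressly reaches worsening in seriousness, so a serious worsening can be left out while the protocol is followed to the letter.

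That carries weight in this population. Under Section 13 patients enter with chest fractures and low inspiratory capacity: "Patients demonstrating the inability to achieve greater than 50% predicted inspiratory capacity based on ideal body weight using IS within the first 24 hours". A pneumothorax already present at entry is not among the exclusions. The protocol names pneumothorax as a hazard of the procedure ("there will be a small risk of a pneumothorax if the intercostal injection needle violates the parietal pleura"), and Section 6 calls for a chest film afterwards only when clinically indicated.

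At stake are the safety comparison and the two stopping rules. The serious-event rule is meant to ignore causality. A discretionary step before the count leaves room for an event to be set aside as part of the original injury.

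**Working it through.** No stated figure needs to be reproduced. The check is a comparison of texts, followed by arithmetic on the stopping rule.

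**1. Texts side by side**

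| Place | Rule for a worsened pre-existing condition |
|---|---|
| Section 6, follow-up | All adverse events recorded; no exception |
| Section 9, opening of Safety Assessments | Every adverse event recorded, related or not; no exception |
| Section 9, definition | Any untoward occurrence; no exception |
| Section 9, pre-existing conditions | Optional, left to the investigator |
| Section 10 | Counts events; silent on this class |

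No passage makes reporting of worsening mandatory, serious or not.

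**2. What falls in the gap**

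- Inside: enlargement of a pneumothorax present at enrolment, and respiratory decline attributed to the original injury.
- Outside: new pneumothorax, new respiratory failure, new arrhythmia and local anesthetic toxicity. None of these was present before enrolment.
- Partly covered: Section 9 makes sustained respiratory-rate and SpO2 changes beyond set limits adverse events by definition. It does not say whether those limits apply beyond the procedure or override the discretion. A pneumothorax that enlarges within the limits would not be caught by them.

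**3. Trigger of the serious-event rule**

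The smallest count exceeding 2% of N enrolled is floor(0.02 × N) + 1.

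| N enrolled | 0.02 × N | Patients needed | One fewer, as % of N |
|---|---|---|---|
| 50 | 1 | 2 | 1/50 = 2.0% |
| 100 | 2 | 3 | 2/100 = 2.0% |
| 150 | 3 | 4 | 3/150 = 2.0% |
| 200 | 4 | 5 | 4/200 = 2.0% |

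In each row, leaving out one patient brings the rate to exactly 2.0%, which does not exceed the limit. For the related-event rule the count at 200 is floor(0.10 × 200) + 1 = 21. An event put down to the original injury would seldom be classed as probably or certainly related, so the exposure lies mainly in the serious-event rule.

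**4. Illustration of sensitivity (assumed rates)**

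The documents give neither a serious-event rate for this trial nor an omission rate. Take a true rate t and a share m of affected patients left uncounted. The chance of at least 5 counted patients in 200 is then 1 − Σ(k = 0 to 4) C(200, k) p^k (1 − p)^(200 − k), with p = t(1 − m).

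| True rate t | m = 0 | m = 25% | m = 50% |
|---|---|---|---|
| 2% | 0.371 | 0.183 | 0.052 |
| 3% | 0.719 | 0.469 | 0.183 |
| 4% | 0.905 | 0.719 | 0.371 |
| 5% | 0.974 | 0.873 | 0.562 |

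This is a single look at 200 patients. Section 10 provides for continuous review, which would change the absolute values but not the direction.

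**5. Arms**

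Under Section 6 the active drug goes next to the intercostal neurovascular bundle and saline goes under the skin over the rib. Aggravation of an existing pneumothorax by the needle would therefore fall mainly on the active arm. The documents give no figure for how often it would occur.

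**The case against.** **General rule and exception.** One sentence speaks of recording and the other of reporting, so the two might be read together as a rule followed by a specific exception. That softens the conflict in drafting terms. It does not close the gap, because the exception decides whether worsening is reported as an adverse event, and Section 10 does not say that events left out this way still count.

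**Scope.** A reader might infer that the exception swallows most of the important harms, or that all patients are exposed because all meet the inspiratory-capacity criterion. The documents do not support either inference. New events are untouched, the physiologic limits cover part of respiratory decline, and meeting the criterion says nothing about the share of harms that could be omitted. The number of patients with a pneumothorax at entry is not given.

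**Direction.** A reader might also infer a demonstrated bias in favour of the active drug. Traumatic pneumothorax can progress in either arm, the trial is described as double-blind, and the discretion clause does not mention causality. An arm difference is plausible, but its size is unknown. The blinding reassures only in part: the injection site differs by arm, so the injecting physician could know the allocation, and the documents do not say that someone else exercises the discretion.

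**Arithmetic.** Any count threshold turns on one event, and at 200 of 200 there is little enrolment left to stop. Both points are fair. The triggers at 50 and 100 patients are the more relevant ones, and they are smaller still.

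**Cost of fuller capture.** This is the strongest point. Prolonged hospitalization is a seriousness criterion, and the 2% rule ignores cause. Section 5 cites mortality of 4 to 20% in blunt chest wall trauma. If 4% applied here (an assumption, since enrolled patients may differ), 0.04 × 200 = 8 deaths would be expected against a trigger of 5, and the chance of reaching it from deaths alone would be 0.905. Complete recording adds to that pressure. It argues for reconciling Sections 9 and 10 together. It does not justify leaving serious worsening to discretion.

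**Conclusion.** The point stands in a limited form. Section 9 leaves worsening of a condition present at enrolment to the investigator's discretion, even when serious. This conflicts with the recording rule in Sections 6 and 9 and with the protocol's own definition of an adverse event. The affected class is narrow but includes progression of an existing pneumothorax.

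Its firm size is the stopping-rule margin: a single omitted patient can decide whether the serious-event rule is met at 2 of 50, 3 of 100 or 5 of 200. This assumes only that the rule is computed on reported events and that the omitted patient has no other counted serious event. The probabilities in the working illustrate sensitivity under assumed rates and do not forecast what will happen. Under-counting is possible under the text as written; the documents do not show that it would be frequent or unequal between arms. I would grade this should-fix.

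**What to change.** Replace the discretion sentence in Section 9 with:

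> Any worsening in severity or seriousness of a pre-existing condition after enrolment will be recorded as an adverse event, and as a serious adverse event if it meets the seriousness criteria.

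In addition:

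- Keep the investigator's assessment of severity and relatedness for each such event.
- State in Section 10 that these events count toward both stopping rules.
- Record baseline chest findings, including any pneumothorax, from the admission CT that Section 6 already uses to locate the fractures, so that worsening is judged against a documented starting point.
- State whether the physiologic limits in Section 9 apply beyond the procedure.

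The cost is a few sentences, a baseline item taken from imaging already obtained, and more adverse event reports. More background trauma morbidity will also count toward the 2% rule. The sponsor should acknowledge this when reconciling Sections 9 and 10; the level of the threshold is outside this point.

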The primary purpose of this pilot study is to compare opioid requirements between groups receiving intercostal liposomal bupivacaine to standard of care for acute traumatic pain related to blunt chest wall trauma with resultant rib and/or sternal fractures. Pain scores will be evaluated using the NRS (Appendix). Uncontrolled analgesia following rib fractures can result in intubation, pneumonia, prolonged length of stay, and death. Achieving adequate pain control in native airway patients prevents clinical challenges. Multimodal analgesia regimens are necessary to optimize patient outcomes and prevent untoward

effects of opioid analgesia. Liposomal bupivacaine offers a novel therapy that may revolutionize pain management in patients with rib fractures. Pain control with one injection may provide analgesia for up to 96 hours through a unique mechanism of action and site of application. Overall, the combination of a nonopioid analgesic, liposomal bupivacaine, with standard of care may lead to improved analgesia with fewer adverse effects. Specific aims include to 1) compare opioid requirements (in morphine equivalents) between patients with blunt chest wall trauma and rib and/or sternal fractures receiving liposomal bupivacaine versus standard of care; 2) compare clinical outcomes and treatment failures including development of pneumonia, median patient analgesia score using verbal NRS, median time to first breakthrough opioid dose, IS ability, ICU LOS, hospital LOS, and use of additional analgesic adjuncts; 4) and to perform a cost-effectiveness analysis

5. Background:

Background and Significance

Blunt chest wall trauma remains the second most common injury observed in non-intentional injury-related death in the U.S.A. and accounts for 10% of trauma-related emergency department visits worldwide.¹⁻³ Current literature has identified high morbidity and mortality rates for patients suffering from blunt chest wall trauma, with mortality ranging from 4 to 20%.^{2,4} The prevalence of rib fractures among blunt chest wall trauma patients requiring hospital admission is 4 to 10%.⁵ One of the most prominent contributing factors to blunt chest wall trauma morbidity is pain.⁶⁻⁸ The management of resultant pain serves as a core intervention in managing these patients.⁸

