Following informed consent, patients will undergo 2x1 block randomization to ensure equal allocation to each intervention group. Randomization will be performed by study personnel and will be blinded as there will be placebo injections for patients randomized into group two and the same number of injections would be used regardless of intervention arm.

Data Collection:

Verbal NRS, pain assessment data, opioid use, and time to first opioid breakthrough dose will be collected as previously described. Portable spirometry will be used daily to objectively and serially assess lung function. Additional data collection points include patient sex, age, weight, body mass index, body surface area, injury severity score, chest abbreviated injury score, and ICU and hospital length of stay. Safety will be evaluated by the occurrence of *a priori* serious adverse events. Costs will be evaluated utilizing hospital and pharmacy databases.

Schedule of subject identification and data collection

Subjects will be identified based on inclusion criteria at the time of admission to the trauma service following evaluation in the emergency department. Subjects meeting inclusion criteria will be enrolled within 6 hours of admission. Vitals monitoring will occur during the intercostal nerve block procedure and continue by telemetry for the next 96 hours or until hospital discharge, whichever occurs first.

7. Specimen collection:

No serum assays are necessary for this study and will not be collected.

8. Potential Benefits:

Blunt chest wall trauma remains a common injury seen in non-intentional injury-related deaths. It accounts for nearly 10% of trauma-related emergency department visits worldwide and is associated with high morbidity and mortality. This morbidity and mortality are influenced by the pain experienced by these events which can involve rib or sternal fractures as instigating stimuli.

Uncontrolled analgesia following rib fractures can result in intubation, pneumonia, prolonged length of stay, and death. Achieving adequate pain control in native airway patients prevents clinical challenges. Multimodal analgesia regimens are necessary to optimize patient outcomes and prevent untoward effects of opioid analgesia (e.g., hypotension; bradycardia; central nervous system depression; respiratory depression).

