Consequences of poorly controlled pain associated with rib and/or sternal fractures as well as opioid use have been previously outlined above. Risks of liposomal bupivacaine include major and minor adverse events (Tables 1 and 2). Risks will be mitigated by appropriate exclusion of patients with low and high body weights as well as known cardiac history as previously described to minimize pharmacodynamic failure or excess.

Table 9.1. Adverse events occurring in >2% of patients in any treatment group^{15,17,31}

Adverse Event	Bunionectomy ^{17, 20}		Hemorrhoidectomy ^{18, 20}	
	Liposomal Bupivacaine 106 mg (n=97)	Placebo (n=96)	Liposomal Bupivacaine 266 mg (n=95)	Placebo (n=94)
Any treatment-emergent adverse event	58 (59.8)	65 (67.7)	16 (16.8)	17 (18.1)
Gastrointestinal disorders				
Nausea	41 (42.3)	38 (39.6)	8 (8.4)	13 (13.8)
Vomiting	39 (40.2)	36 (37.5)	2 (2.1)	1 (1.1)
Painful defecation	27 (27.8)	17 (17.7)	2 (2.1)	4 (4.3)
Nervous system disorders				
Dizziness	20 (20.6)	30 (31.3)	0 (0.0)	0 (0.0)
Headache	11 (11.3)	25 (26.0)	0 (0.0)	0 (0.0)
Somnolence	5 (5.2)	8 (8.3)	0 (0.0)	0 (0.0)
Skin and subcutaneous tissue disorders				
Skin and subcutaneous tissue disorders	8 (8.2)	7 (7.3)	0 (0.0)	0 (0.0)
Pruritus, generalized	5 (5.2)	6 (6.3)	0 (0.0)	0 (0.0)
Abnormal laboratory investigations	5 (5.2)	3 (3.1)	4 (4.2)	3 (3.2)

Data are no. (%) of patients.

Table 9.2. Incidence of serious adverse events occurring in >1 patient in any treatment group³⁰

	n (%)		
	Liposome Bupivacaine		
	≤266 mg (n = 545)	Bupivacaine HCl (n = 446)	Placebo (n = 190)
Any serious AE	6 (1.1)	24 (5.4)	2 (1.1)
Arthrofibrosis	0	3 (0.7)	0
Cellulitis	0	0	0
Congestive cardiac failure	0	0	0
Atrial fibrillation	0	2 (0.4)	0
Sedation	0	0	0
Hypoglycemia	0	2 (0.4)	0
Deep vein thrombosis	0	2 (0.4)	1 (0.5)

Cardiac and neurotoxicity that are generally seen with increased serum bupivacaine concentrations (i.e. >2000 ng/mL) should serve minimal risk as concentrations seen in previous studies using the maximum FDA-approved dose of 266 mg of liposomal bupivacaine measured maximum concentrations of 867 and <300 ng/mL each.^{15, 28-29} Patients will require and be monitored by a central cardiac monitoring unit to assess for any changes in heart rate or rhythm for the first 96 hours at minimum.

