An adverse event (also referred to as an adverse experience) can be any unfavorable and unintended sign (e.g., an abnormal laboratory finding), symptom, or disease temporally associated with the use of a drug, and does not imply any judgment about causality. An adverse event can arise with any use of the drug (e.g., off-label use, use in combination with another drug) and with any route of administration, formulation, or dose, including an overdose.

Suspected Adverse Reaction

Suspected adverse reaction means any adverse event for which there is a reasonable possibility that the drug caused the adverse event. For the purposes of IND safety reporting, 'reasonable possibility' means there is evidence to suggest a causal relationship between the drug and the adverse event. A suspected adverse reaction implies a lesser degree of certainty about causality than adverse reaction, which means any adverse event caused by a drug.

Adverse Reaction

An adverse reaction means any adverse event caused by a drug. Adverse reactions are a subset of all suspected adverse reactions where there is reason to conclude that the drug caused the event.

Unexpected

An adverse event or suspected adverse reaction is considered “unexpected” if it is not listed in the investigator brochure or is not listed at the specificity or severity that has been observed; or, if an investigator brochure is not required or available, is not consistent with the risk information described in the general investigational plan or elsewhere in the current application, as amended.

Serious

An adverse event or suspected adverse reaction is considered “serious” if, in the view of either the investigator or sponsor, it results in any of the following outcomes: Death, a life-threatening adverse event, inpatient hospitalization or prolongation of existing hospitalization, a persistent or significant incapacity or substantial disruption of the ability to conduct normal life functions, or a congenital anomaly/birth defect. Important medical events that may not result in death, be life-threatening, or require hospitalization may be considered serious when, based upon appropriate medical judgment, they may jeopardize the patient or subject and may require medical or surgical intervention to prevent one of the outcomes listed in this definition.

Life-Threatening

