 - c. Median time to first breakthrough opioid rescue dose
 - d. Incentive spirometry serial volume capacity
 - e. ICU LOS
 - f. Hospital LOS
 - g. Use of additional analgesia adjuncts
 - i. Epidural catheter
 - ii. Non-opioid analgesics (e.g., non-steroidal anti-inflammatory drugs; gabapentin; pregabalin; carbamazepine; ketamine; acetaminophen)
- 2) Perform a cost-effectiveness analysis
- 3) Calculate dose and exposure of lidocaine or bupivacaine over time from Lidoderm patches, intercostal nerve blocks, or epidural catheters

Statistical analyses will be performed using SAS. An intention-to-treat model will be used for data analysis. Patients randomized into the treatment arm will be included in the primary outcome analysis. Patients withdrawn from the study will have data included up to the point of withdrawal. Nominal data will be reported using frequencies of occurrence and proportions as appropriate. Continuous data will be reported using means and standard deviations or medians and

interquartile ranges as appropriate per distribution. Hypothesis testing for nominal data will be performed using the Fisher's exact test or chi square test as required based on sample size. Continuous data will be compared using student's t-test/ANOVA or rank sum/Kruskal-Wallis ANOVA for normally distributed and non-normally distributed data, respectively as appropriate. A p-value < 0.05 will designate statistical significance. Costs associated with the cost-effectiveness analysis will be pulled from hospital and pharmacy databases.

Given the pilot nature of the study, a total of 200 patients will be enrolled. Assuming a 96-hour requirement of 250-mg oral morphine equivalents (approximately 12.5-mg IV hydromorphone), we anticipate a 20% reduction to 200-mg oral morphine equivalents (approximately 10-mg IV hydromorphone) resulting in an expected difference in means of 50 mg and an anticipated standard deviation of 50 mg. To achieve an 80% power with an alpha of 0.05 for this primary outcome, the goal enrollment is 200 patients.

12. Data storage and confidentiality (include sample storage if applicable)

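### The all-cause 2% stopping rule does not say which enrolled patients form the denominator and is not reconciled with the quoted background risk, so it can end a trial of a harmless drug

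*Combined protocol and SAP*

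**What the plan says.** Section 10 gives two conditions under which the study will be stopped. One concerns events judged probably or certainly drug-related, at more than 10% of enrolled patients. The other, at issue here, is that "Serious/life-threatening adverse events, regardless of causality, occur in > 2% of enrolled patients". On timing, "Adverse events will be continuously assessed on an ongoing basis by" the medical monitor. The section gives no minimum number, schedule of looks, comparison between arms or expected rate.

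Section 9 calls an event serious if "it results in any of the following outcomes: Death, a life-threatening adverse event, inpatient hospitalization or prolongation of existing hospitalization", among other outcomes, and defines life-threatening separately. It also limits what is reported: "Any medical condition present prior to study enrollment should not be reported as an adverse event, unless the medical condition worsens". Section 5 describes blunt chest wall trauma "with mortality ranging from 4 to 20" percent. Section 4 names intubation, pneumonia, prolonged stay and death as possible results of poorly controlled rib-fracture pain.

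The only serious-event rates in the document are in Table 9.2, in the row "Any serious AE": 1.1% on liposomal bupivacaine (6/545), 5.4% on bupivacaine HCl (24/446) and 1.1% on placebo (2/190). They come from earlier trials of the product, not from trauma patients.

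**The concern.** The rule counts events of any cause in both arms together, so the complications of the injury use up the 2% allowance whether or not the drug does harm. If the background rate is near or above 2%, the likely result is a mandatory stop that says nothing about the drug.

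How soon it comes depends on a choice the text leaves open. On the to-date reading the trial could end after a few dozen patients, too few for the opioid comparison. On the planned-200 reading a stop comes later, and on the protocol's own inputs the loss is mainly planned enrollment and safety and secondary data. Two careful monitors could apply the same sentence and reach different decisions.

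**Working it through.** **Inputs.** Limit above 2%, continuous assessment (Section 10). Planned 200, 100 per arm (Sections 5 and 11). Mortality 4 to 20% (Section 5). Placebo serious-event rate 1.1% (Table 9.2). For power, "an expected difference in means of 50 mg and an anticipated standard deviation of 50 mg" (Section 11), with a two-sided 0.05 test assumed. The event rates of 1.1%, 2%, 3% and 4% are assumptions, taken as equal in both arms and independent between patients.

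**The plan's own figures.** The 2% limit has no derivation, so there is nothing to reproduce. The sample size can be checked: n per arm = 2 × (1.960 + 0.842)² × (50/50)² = 15.7, so 16 per arm or 32 in total. With the t-test, power is 78.1% at 32 patients and 80.7% at 34. The stated 200 does not follow from these inputs. The SD at which 100 per arm gives 80% power is 50 / [√(2/100) × 2.802] ≈ 126 mg.

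**Where the limit bites.** To date: 1/49 = 2.04% exceeds 2% and 1/50 = 2.00% does not, so any event among the first 49 patients stops the study. Planned 200: 0.02 × 200 = 4, so the fifth patient with an event stops it. For comparison, 4% and 20% of 200 are 8 and 40 patients.

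**Chance of stopping with no drug effect.** Planned 200: 1 − P(X ≤ 4), X ~ Binomial(200, p). To date: an exact patient-by-patient recursion that stops when events exceed 0.02n, for n = 1 to 200, with each outcome known at once. Average power is t-test power at the stopping patient, weighted by the stopping distribution (50 mg difference, 50 mg SD).

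| Assumed rate | To date: stop by 200 | To date: stop before 34 | To date: average power | Planned 200: stop by 200 | Planned 200: stop before 34 | Planned 200: average power |
|---|---|---|---|---|---|---|
| 1.1% | 51.8% | 31% | 81% | 7.1% | <0.1% | >99.9% |
| 2% | 80.3% | 49% | 69% | 37.1% | <0.1% | 99.9% |
| 3% | 94.2% | 63% | 59% | 71.9% | 0.3% | 99.6% |
| 4% | 98.6% | 74% | 51% | 90.5% | 1% | 98.8% |

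Hand check at 4%, to date: 1 − 0.96¹⁶ = 0.480 and 1 − 0.96¹⁷ = 0.500, so the median stop is patient 17, where power is 48.6%. Under planned 200 the median stop at 4% is patient 117.

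**Sensitivity, at 4% unless stated.**
- Assumed 10-patient reporting lag, to date: 97.8% stopped, median patient 27, 61% stopped before patient 34, average power 70%.
- Monitoring first applied at patient 50 or 100, to date: 97.9% or 97.1% still stop. At a 1.1% rate the figures are 36% and 26%.
- SD of 126 mg in place of 50 mg: average power 17 to 18% (to date, immediate reporting) or 56% (planned 200).

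**The case against.** The words on causality show that an all-cause limit was deliberate. Section 5 says this use has been studied only in case reports and preliminary work, so a cautious limit beside the separate drug-related rule is a legitimate choice. Any pooled all-cause limit can stop a harmless trial. That stands as a defense of having such a limit. It does not settle the denominator, or show that 2% was chosen with a background rate in view. The 10% rule is a separate trigger and does not relax this one.

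The quoted mortality is for blunt chest wall trauma generally. The trial excludes recent intubation, hemodynamic instability, active myocardial ischemia and GCS below 8, so its rate may be lower. Inclusion criterion (c), poor inspiratory capacity, may raise it. This objection stands: a reader might infer that Sections 5 and 10 contradict each other, but the documents give no rate for the enrolled population that would prove it.

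Two other strong readings also fail. A reader might infer that the rule has no denominator at all; it names enrolled patients, and only the meaning of that phrase is open. A reader might infer that the countable events are undefined. Section 6 does say "Safety will be evaluated by the occurrence of" a priori serious adverse events without listing them, but Section 9 defines both serious and life-threatening. What remains unclear is whether the slash between the two words means either or both. No reading removes deaths or new life-threatening events.

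Finally, the power figures rest on inputs that do not yield the plan's own sample size, and patient 17 assumes instant reporting. Both points stand, and the power results are conditional on them.

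**Conclusion.** The point holds as a mismatch that should be fixed, with moderate confidence. The size of the problem turns on the unstated denominator. At an assumed 1.1%, a harmless drug is stopped in about half of trials on one reading and in 7% on the other. At 4%, the lowest mortality the protocol quotes, a stop is probable on both. A minimum number alone does not cure this.

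A reader might infer that the rule ruins the primary comparison whatever the denominator. On the protocol's 50 mg difference and 50 mg SD that is not so: serious loss of power is confined to the to-date reading. With an SD near 126 mg both readings lose power, but the documents do not state that SD. The stopping probabilities do not depend on the SD. They rest on the assumed event rates, independence between patients and, for the to-date results in the table, immediate reporting.

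**What to change.** Reconcile the limit in Section 10 with the background risk quoted in Section 5. In Section 10:

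1. State whether the denominator is patients enrolled to date or the planned 200, and when monitoring against the limit begins.
2. Say whether the combined term means serious or life-threatening, or both at once.
3. Set the limit against a stated expected serious-event rate for this population. Confidential arm-level review by the medical monitor could be added. With so few events a between-arm comparison has little power, so it supplements the limit and does not replace it.
4. Report the probability of a false stop at the expected rate.

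The sponsor and medical monitor set the tolerances; no threshold is proposed here. The cost is protocol wording and a short boundary calculation. The downside is that the study may no longer stop automatically on the first serious event, and any arm-level counts must be supplied confidentially to protect the blind.
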